### LIST OF ABBREVIATIONS AND RELEVANT DEFINITIONS

ABR	General Assessment and Registration
	form (ABR form), the application form
	that is required for submission to the
	accredited Ethics Committee; in Dutch:
	Algemeen Beoordelings- en
	Registratieformulier (ABR-formulier)
AE	Adverse Event
AR	Adverse Reaction
AZ	AstraZeneca
NT-proBNP	N-Terminal Prohormone of Brain
	Natriuretic Peptide
CA	Competent Authority
ССМО	Central Committee on Research
	Involving Human Subjects; in Dutch:
	Centrale Commissie Mensgebonden
	onderzoek
CRP	C-Reactive Protein
cv	Curriculum Vitae
DSMB	Data Safety Monitoring Board
eGFR	Estimated glomerular filtration rate
EU	European union
EudraCT	European drug regulatory affairs Clinical
	Trials
GCP	Good Clinical Practice
GDPR	General Data Protection Regulation; in
	Dutch: Algemene Verordering
	Gegevensbescherming (AVG)
GLP-1	Glucagon-like Peptide-1
IB	Investigator's Brochure
IC	Informed Consent
IMP	Investigational Medicinal Product
IMPD	Investigational Medicinal Product
	Dossier

METC	Medical research ethics committee
	(MREC); in Dutch: medisch-ethische
	toetsingscommissie (METC)
NSAIDs	Nonsteroidal anti-inflammatory drugs
(S)AE	(Serious) Adverse Event
SGLT2	Sodium Glucose Transport Inhibitor 2
SPC	Summary of Product Characteristics; in
	Dutch: officiële productinformatie IB1-
	tekst
Sponsor	The sponsor is the party that
	commissions the organization or
	performance of the research, for
	example a pharmaceutical company,
	academic hospital, scientific
	organization or investigator. A party that
	provides funding for a study but does
	not commission it is not regarded as the
	sponsor but referred to as a subsiding
	party.
SUSAR	Suspected Unexpected Serious Adverse
	Reaction
UAVG	Dutch Act on Implementation of the
	General Data Protection Regulation; in
	Dutch: Uitvoeringswet AVG
UACR	Urine albumin-to-creatinine ratio
WMO	Medical Research Involving Human
	Subjects Act; in Dutch: Wet Medisch-
	wetenschappelijk Onderzoek met
	mensen
	I .

### **SUMMARY**

### Rationale:

Persistent increased albuminuria is a strong risk marker for progressive kidney disease and cardiovascular disease in patients with or without diabetes. The degree of albuminuria reduction in the first months of treatment with pharmacological or dietary intervention correlates with the degree of long-term (3 to 4 years) renal or cardiovascular protection. Despite the various available treatments to decrease urinary albumin excretion, residual albuminuria persists in many patients. The high residual albuminuria in a proportion of patients is at least in part explained by suboptimal response to the current treatments (i.e., ACE inhibitor or Angiotensin Receptor Blockers).

Dapagliflozin is a sodium-glucose transport inhibitor and inhibits the reabsorption of glucose in the proximal tubule. This leads to a decrease in fasting plasma glucose and HbA1c in patients with type 2 diabetes. In addition, dapagliflozin administration causes a decrease in blood pressure and body weight and an increase in hematocrit suggestive of a diuretic effect. Previous studies have also demonstrated the albuminuria lowering effects of dapagliflozin in patients with type 2 diabetes mellitus.

Although dapagliflozin markedly slows progression of kidney function decline (and reduces cardiovascular outcomes) on a population level, randomized parallel group trials have suggested a marked variation in the response to dapagliflozin between individual patients. By design, randomized parallel group placebo-controlled clinical trials test the efficacy of new interventions on a population level but do not assess the efficacy of a drug for the individual. Although there is variation in response between patients, parallel group trial does not allow conclusions whether this variation is a true variation in drug response, or measurement or temporal random variation. We therefore propose a crossover trial with repeated administration (i.e., a series of N=1 trials) to ascertain the individual drug response. This design specifically allows for assessment of drug efficacy and safety at an individual level.

### Objective:

- Primary:
  - To determine the individual response to the SGTL2 inhibitor dapagliflozin in urine albumin-to-creatinine ratio (UACR)
- Secondary:
  - o To determine the individual response to the SGLT2 inhibitor dapagliflozin

in:

- Systolic blood pressure
- Body weight
- eGFR
- Fasting plasma glucose

### Study design:

Randomized placebo-controlled double-blind cross-over N=1 trial. Eligible participants will be invited for screening. After a screening visit, eligible patients will be randomly assigned to a cross-over study consisting of two periods of 1-week treatment with dapagliflozin and two periods of 1-week treatment with placebo in random order with a 1-week wash-out period between every treatment period to avoid cross-over effects. Based on a prior study where patients were exposed to dapagliflozin 10 mg, effects of dapagliflozin on UACR, blood pressure, body weight, eGFR and plasma glucose were fully present after 1 week and returned to baseline 4 days after drug discontinuation. Hence, a 1-week treatment followed by 1 week wash-out is considered sufficient to detect treatment effects.

### **Study population:**

Adult male and female patients with UACR >20 mg/g (2.26 mg/mmol) with type 2 diabetes mellitus treated in primary or secondary healthcare. Subjects will be recruited via general practitioner practices and via the outpatient clinic of the Department of Internal Medicine of the Ziekenhuisgroep Twente, Almelo.

### Intervention:

Dapagliflozin 10 mg/day

### Main study parameters/endpoints:

Difference in change in first morning void UACR from start to end of treatment between dapagliflozin and placebo exposure.

Nature and extent of the burden and risks associated with participation, benefit and group relatedness:

The efficacy and safety of dapagliflozin is established in multiple parallel randomized controlled trials involving more than 25,000 patients with type 2 diabetes. Urinary tract infections and genital infections are the most frequently reported side effects. Dapagliflozin reduces body weight unlike sulfonylurea derivatives and insulin.

Participants visit the outpatient clinic at three occasions (i.e., a screening visit, a second visit and end of study visit) and have to record body weight and blood pressure at home and collect blood and urine at home.

Blood pressure and body weight are measured at home by the participants using ambulant devices (Withings BPM Connect and Withings Body+, respectively). Participants measure their blood pressure and body weight once daily on 28 and 40 days in total, respectively. Capillary blood will be sampled at home by participants using a BD Microtainer® Contact-Activated Lancet (once daily on 22 days in total). Blood is collected with the Hem-Col® device, which is designed to collect capillary blood drawn with a finger prick. In order to make patients comfortable with the blood collection procedures, they first collect a capillary blood sample at the study site during the second visit under supervision of trained lab technicians. A venous blood sample will also be taken during the second visit in order to compare the clinical chemistry assessments in capillary blood with those measured in venous blood samples (NL70447.100.19). Participants will be asked to draw blood samples at home by a finger prick and send the samples to the laboratory. Participants will collect first morning void urine samples through the PeeSpot® device (once daily on 40 days in total) which allows for decentralized urine collection in a small tube. The urine tubes and blood samples will be sent by regular mail to the laboratory. No other invasive measurements will be executed.

The advantage of an N=1 study is that efficacy of the intervention is vetted for the actual participant. Dapagliflozin is currently marketed in the Netherlands and recommended in patients with type 2 diabetes mellitus and eGFR>45 mL/min/1.73m². Patients who show a satisfactory response to dapagliflozin and whose characteristics fulfill the criteria according to which dapagliflozin can be prescribed in clinical practice are offered to receive dapagliflozin after the study. It is expected that the indication for dapagliflozin will be broadened to patients with eGFR 25-45 mL/min/1.73m² in the near future. If this occurs, these patients can also be treated on-label in practice.

The expected time investment for participants is 20 hours, including measurements at home. Participants receive restitution of travel costs to visit the outpatient clinic for the screening, randomization and end of study visit. Participants receive no priority in treatment of other diseases in the clinic during this study. Participation in this study is on a free-will base. Participants can keep the body weight scale and blood pressure device at the end of the study.

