### 1. INTRODUCTION AND RATIONALE

The sodium-glucose co-transporter 2 (SGLT2) is found primarily in the S1 segment of the proximal tubule of the kidney and accounts for 90% of the glucose reabsorption in the kidney in order to maintain appropriate glucose levels. SGLT2 transports one ion of Na+ per molecule of glucose. Because Na+ is actively extruded by Na/K-ATPase, the extracellular Na+ concentration substantially exceeds the intracellular concentration. Movement of Na+ down its electrochemical gradient provides the energy required for active transport of glucose. SGLT2 inhibitors reversely inhibit the SGLT2-transporter, leading to an increase in urinary glucose and sodium excretion by reducing glucose reabsorption in the renal proximal tubule. Initial relatively short-term studies (up to 52 weeks) have shown that SGLT2 inhibitors exert beneficial effects on multiple cardiovascular risk markers including HbA1c, blood pressure, body weight, and uric acid. Large clinical trials have shown that SGLT2 inhibitors reduce the risks of heart failure and kidney failure in patients with (or without) type 2 diabetes mellitus (T2DM).

Persistent increased albuminuria is an established risk marker for development of chronic kidney disease and cardiovascular disease events in patients with or without type 2 diabetes. Prior studies have shown that SGLT2 inhibitors reduce the urine albumin-to-creatinine ratio (UACR). These UACR-lowering effects of SGLT2 inhibitors tend to be greater with higher levels of baseline UACR. Prior studies have shown that the SGLT2 inhibitor dapagliflozin reduces UACR in patients with T2DM. The UACR reduction achieved with dapagliflozin was independent of concomitant changes in HbA1c, blood pressure, eGFR or uric acid, suggesting a direct mechanism of action.

More recently, the DAPA-CKD trial reported the efficacy and safety of dapagliflozin in 4,304 patients with chronic kidney disease with or without type 2 diabetes. The trial demonstrated that dapagliflozin significantly reduced the risk of kidney and cardiovascular endpoints, prolonged survival and reduced the UACR. Furthermore, dapagliflozin was well tolerated in keeping with the established safety profile. No major hypoglycemic events were reported in these patients.

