### 6.4. Summary of known and potential risks and benefits

The primary assessment of safety and tolerability of dapagliflozin was conducted in a pre-specified pooled analysis of 13 short-term (up to 24 weeks) placebo-controlled studies with 2,360 subjects treated with dapagliflozin 10 mg and 2,295 with placebo. Of the 17,160 patients in the dapagliflozin cardiovascular outcome study, 8,574 patients received dapagliflozin 10 mg and 8,569 received placebo for a median exposure time of 48 months. In total, there were 30,623 patient-years of exposure to dapagliflozin. The most frequently reported adverse reactions across the clinical studies were genital infections.

The overall incidence of adverse events (short-term treatment) in subjects treated with dapagliflozin 10 mg was similar to placebo. Few adverse events led to discontinuation of treatment and were balanced across study groups. The most commonly reported events leading to discontinuation in patients treated with dapagliflozin 10 mg were increased blood creatinine (0.4%), urinary tract infections (0.3%), nausea (0.2%), dizziness (0.2%), and rash (0.2%).

The most frequently reported adverse reaction was hypoglycemia, which depended on the type of background therapy used in each study. The frequency of minor episodes of hypoglycemia was similar between treatment groups, including placebo, with the exceptions of studies with add-on sulphonylurea and add-on insulin therapies. Combination therapies with sulphonylurea and add-on insulin had higher rates of hypoglycemia.

In the 13-study safety pool, vulvovaginitis, balanitis and related genital infections were reported in 5.5% and 0.6% of subjects who received dapagliflozin 10 mg and placebo, respectively. Most infections were mild to moderate, and subjects responded to an initial course of standard treatment and rarely resulted in discontinuation from dapagliflozin treatment. These infections were more frequent in females (8.4% and 1.2% for dapagliflozin and placebo, respectively), and subjects with a prior history were more likely to have a recurrent infection.

In the dapagliflozin cardiovascular outcomes study, the number of patients with serious adverse events of genital infections were few and balanced: 2 patients in each of the dapagliflozin and placebo groups.

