# b. Previous exposure of human being with the test product(s) and/or products with a similar biological mechanism

Previously, twelve phase 3 randomized controlled clinical trials were conducted involving more than 6000 patients with type 2 diabetes mellitus of whom ~4000 were treated with dapagliflozin. Eleven studies were 24-weeks in duration with extension in 6 studies up to 78 weeks. One study was 52 weeks in duration with extension of another 52 weeks.

More recently, the DAPA-CKD trial reported the efficacy and safety of dapagliflozin in 4,304 patients with chronic kidney disease with or without type 2 diabetes. The trial demonstrated that dapagliflozin significantly reduced the risk of kidney and cardiovascular endpoints and prolonged survival. Dapagliflozin was well tolerated in keeping with the established safety profile. Specifically, in this population there was no diabetic ketoacidosis with dapagliflozin. In patients with CKD without type 2 diabetes no major hypoglycemic events were reported.

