#### d. Selectivity of the mechanisms to target tissue in animals and/or human beings

#### e. Analysis of potential effect

In placebo controlled clinical trials the following adverse reactions have been identified:

- Infections and infestations: vulvovaginitis, balanitis and related genital infections, urinary tract infections (common); fungal infection (uncommon)
- Metabolism and nutrition disorders: hypoglycemia (when used with SU or insulin) (very common); volume depletion (uncommon)
- Nervous system disorders: dizziness (common)
- Gastrointestinal disorders: constipation, dry mouth (uncommon)
- Skin and subcutaneous tissue disorders: rash (common)
- Musculoskeletal and connective tissue disorders: back pain (common)
- Renal and urinary disorders: dysuria, polyuria (common); nocturia (uncommon)
- Reproductive system and breast disorders: vulvovaginal pruritis, pruritus genital (uncommon)
- Investigations: hematocrit increased, creatinine renal clearance decreased during initial treatment, dyslipidemia (common); blood creatinine increased during initial treatment, blood urea increased, weight decreased (uncommon).

Common (>1/100 to <1/10) and uncommon (>1/1000 to <1/100)

Few adverse events led to discontinuation of treatment and adverse events were balanced across study groups. The most commonly reported events leading to discontinuation in patients treated with dapagliflozin 10 mg/day were increased blood creatinine (0.4%), urinary tract infections (0.3%), nausea (0.2%), and rash (0.2%). It should be noted that the transient rise in serum creatinine may reflect a reduction in intra-glomerular pressure which may be associated with long-term structural renal protection.

A pooled analysis of 3152 patients who received dapagliflozin in doses between 2.5 and 10 mg/day showed that the incidence of urinary tract infection was increased with dapagliflozin dosage. Most diagnosed infections were mild to moderate and responded to standard antimicrobial treatment.

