#### j. Can effects be managed?

Patients are regularly monitored and asked about adverse effects of urinary tract infections or infestations. As reported above, dapagliflozin administration is associated with an increased risk of infections which can be managed with standard antimicrobial treatment.

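### The Summary's risk statement omits hypoglycaemia, the protocol ranks it inconsistently elsewhere, and the only directed enquiry described concerns infections, so hypoglycaemia is captured passively

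*Combined protocol and SAP*

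**What the plan says.** The documents describe the frequency of adverse reactions in several places:

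- **Protocol Summary, burden and risks:** "Urinary tract infections and genital infections are the most frequently reported side effects". Hypoglycaemia is not mentioned there.
- **Protocol 6.4, first paragraph:** "The most frequently reported adverse reactions across the clinical studies were genital infections".
- **Protocol 6.4, third paragraph:** "The most frequently reported adverse reaction was hypoglycemia, which depended on the type of background therapy used in each study". It adds that minor episodes were otherwise similar between groups, and that "Combination therapies with sulphonylurea and add-on insulin had higher rates of hypoglycemia".
- **Protocol 13.1 e:** "hypoglycemia (when used with SU or insulin) (very common"), while genital and urinary tract infections are classed as common.
- **Protocol 1, on the trial in chronic kidney disease with or without type 2 diabetes:** "No major hypoglycemic events were reported in these patients". Section 6.3 says the same without restriction. Section 13.1 b words it more narrowly: "In patients with CKD without type 2 diabetes no major hypoglycemic events were reported".

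On enquiry, protocol 13.1 j says: "Patients are regularly monitored and asked about adverse effects of urinary tract infections or infestations". Protocol 9.2.1 has all adverse events recorded, whether volunteered by the patient or noticed by staff. Protocol 3 and SAP 3.1 allow patients to enter adverse events in Selfcare. SAP 6 plans counts and percentages by treatment arm for categorical safety indicators.

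**The concern.** Every participant has type 2 diabetes and takes the study drug at home. Insulin and sulphonylurea appear neither among the exclusions in protocol 4.3 nor among the disallowed treatments in 5.2, and 5.2 itself acknowledges a hypoglycaemia risk when they are combined with dapagliflozin. The protocol therefore knows of the risk but leaves it out of the short statement from which a reader would judge burden and risk.

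The described enquiry follows the same pattern: infections are asked about, while hypoglycaemia is left to be volunteered. Solicited and unsolicited events are not recorded with the same completeness. A trial that aims to describe efficacy and safety in the individual patient would have a weaker record of one reaction than of another that its own risk analysis ranks as less frequent in insulin or sulphonylurea users.

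**Working it through.** **1. Ranking of reactions.** Section 13.1 e defines common as above 1/100 and below 1/10. Section 6.4 gives genital infections in 5.5% on dapagliflozin and 0.6% on placebo in the 13-study pool. Since 1% < 5.5% < 10%, that rate agrees with the class common. Very common is not defined; its place above common is inferred from the ordering of the classes. On the protocol's own scale, hypoglycaemia in sulphonylurea or insulin users therefore ranks above the infections. No percentage for hypoglycaemia is given anywhere, so the difference has no numerical size.

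**2. Consistency of the statements.** The Summary agrees with the first paragraph of 6.4 on genital infections, but not with the third paragraph. The two paragraphs of 6.4 name different reactions as most frequent. They may refer to different data sets (all studies against the short-term pool), but the text does not say so.

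**3. Scheduled glucose readings.** The schedule in protocol 3 gives:
- run-in: Days -7 and -1, 2 readings;
- four treatment periods with Days 1, 6 and 7: 4 × 3 = 12;
- four wash-outs with Days 6 and 7: 4 × 2 = 8;
- total: 2 + 12 + 8 = 22, which reproduces the 22 capillary sampling days in the Summary.

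Per patient there are 2 × 7 = 14 dapagliflozin days. Of these, 2 × 3 = 6 have a scheduled fasting reading (6/14 = 43%) and 14 − 6 = 8 have none. Each reading is a single fasting value, so it is not a record of episodes at other times of day.

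**4. Scheduled contacts.** Calls are on Days 3 and 6 of the first two treatment periods: 2 × 2 = 4 calls, with none in periods 3 and 4. Their stated purpose is compliance with procedures. The clinic visits are screening, the second visit and end of study.

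**5. Routes of capture.**

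| Reaction | Volunteered or observed | Selfcare entry | Scheduled measurement | Directed question described |
|---|---|---|---|---|
| Infections | yes | yes, optional | no | yes (13.1 j) |
| Hypoglycaemia | yes | yes, optional | fasting glucose, 22 days | no |

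The documents contain no definition of a hypoglycaemic event, no request for a reading when symptoms occur, and no named hypoglycaemia line in SAP 6.

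**The case against.** The best defence is that this is background wording and that hypoglycaemia is captured. Much of that stands. Section 9.2.1 covers all adverse events, Selfcare gives patients a direct route, and every participant has a glucose meter, their own or a supplied one, with results going to Selfcare. Section 13.1 j answers a risk-analysis question and is not the adverse-event procedure; it does not say that nothing else is asked. The risk is also disclosed in sections 5.2, 6.4 and 13.1 e. Reporting is double-blind, so there is no evident reason for under-recording to differ between dapagliflozin and placebo weeks.

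Some stronger readings are tempting but are not supported:

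- **That hypoglycaemia is the main risk of the trial.** The text supports only a frequency ranking among insulin or sulphonylurea users; section 6.4 says minor episodes were otherwise similar to placebo.
- **That SAP 6 cannot compare it between treatments.** Any recorded event would fall within the generic counts.
- **That a number of affected patients can be predicted.** Neither the count of insulin or sulphonylurea users nor a hypoglycaemia rate is given. The safety pool runs up to 24 weeks (24 × 7 = 168 days), against 14 dapagliflozin days here, a twelvefold difference.
- **That sections 1 and 6.3 contradict 13.1 b.** No events in patients with or without diabetes is compatible with no events in those without. The scope is merely unclear, and the narrower wording offers no reassurance for this population.
- **That participants are not told.** The consent pages are not available, so nothing can be inferred.

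**Conclusion.** The point holds as a modest one about consistency and safety capture. The Summary omits a reaction that section 6.4 in one place calls the most frequent and that 13.1 e ranks above infections in patients who may enrol. Hypoglycaemia is captured passively, while infections are, as far as the text describes, solicited. The measurable part of the gap is 8 of 14 dapagliflozin days per patient without a scheduled glucose reading, and two of four treatment periods without a scheduled call. How many events would be missed cannot be derived from the documents. The conclusion assumes that the enquiry in 13.1 j is described in full; if site procedures already ask about hypoglycaemia, only the wording needs repair. Wording alone would be clerical. The added prompt is what makes the change worthwhile.

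**What to change.** 1. Reconcile the Summary and protocol 6.4 and 13.1 e into one account of hypoglycaemia risk for this population, stating which data set each frequency statement refers to. Clarify the scope of the statement on major hypoglycaemic events in sections 1, 6.3 and 13.1 b.
2. Name hypoglycaemia beside infections in the enquiry in 13.1 j, and make it a prompted item on the Selfcare adverse-event form in all four treatment periods. Selfcare is needed because the scheduled calls stop after the second period.
3. List hypoglycaemia by treatment received in the SAP 6 safety table, since every patient who completes the trial receives both treatments. A split by background therapy is not needed: with 20 patients its cells would be nearly empty.

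The cost is protocol wording, one extra prompted question for patients and one table line. None of this proposes a rule for dosing or for managing hypoglycaemia.
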